4.2 SCIENTIFIC RATIONALE FOR STUDY DESIGN

The study design and procedures were chosen to assess the effect of 14 days of treatment on glucagon response to insulin-induced hypoglycemia. The study design allows an ample wash out time to minimize the risk of carry-over effects before crossing over the two groups.

A hypoglycemic clamp has been chosen to evaluate the response to hypoglycemia during treatment. It is acknowledged by the field that a hypoglycemic clamp does not fully recapitulate all aspects of clinical episodes of hypoglycemia occurring under conditions of daily life (such as effects of stress, physical activity, altered food intake or variation in insulin dose and its subcutaneous absorption). However, it is a controlled, reproducible platform enabling delineation of the counter-regulatory hormonal response and lends itself as particularly suitable for paired, within-subject evaluations as we propose to do in evaluating the pharmacology of a GPR119 agonist on glucagon counter-regulation.

While our primary goal will be to examine an effect on glucagon counter-regulation in T1DM, we also propose to examine any effects on fasting and postprandial glucagon, as well as upon incretin secretion (GLP-1 and GIP). We acknowledge that it is improbable much effect upon hyperglycemia will be observed in T1DM, given the severity of the deficiency in insulin secretion in T1DM, and given that the effect in T2DM was only modest. Yet, the testing is important for several reasons. Firstly, if a GPR119 agonist were to elevate glucagon in T1DM under fasting and postprandial conditions, this would be quite unfavorable and thus important to know early in its evaluation. Increases in incretin secretion in T1DM (as have been observed with DPP-4 inhibitors) could also be potentially favorable, perhaps especially for increased GIP which can mitigate risk of hypoglycemia by bolstering glucagon counter-regulation to hypoglycemia; this might be most relevant to mitigation of risk for postprandial episodes hypoglycemia in T1DM.

4.3 JUSTIFICATION FOR DOSE

The dose proposed for this study is 600 mg of MBX-2982 as the HCl salt formulation. Though the dose-response relationship for MBX-2982 and stimulation of insulin and incretin secretion has been described,

it is uncertain whether this pertains equally to a stimulatory effect on glucagon counter-regulation during hypoglycemia. In consideration that the current proposal will be the first study of potential clinical translation of this effect previously observed in rodent and the safety of the medication, a dose that achieves high exposure of MBX-2982 was chosen to ensure a high level of GPR119 target engagement. If positive findings are obtained, consideration will be given to a supplemental study to delineate if doses lower (and higher) than 600 mg daily achieve similar or accentuated stimulatory effect on glucagon counter-regulation during hypoglycemia.

4.4 END OF STUDY DEFINITION

A participant is considered to have completed the study if he or she has completed all phases of the study including the end of trial visit seven days after the last dose of the study medication as shown in the Schedule of Activities (SoA).

4.5 STUDY SITE(S)/LOCATION(S) AND NUMBER OF SUBJECTS

The study will be conducted at two centers with AdventHealth Orlando, Translational Research Institute serving as the principal site. The participating centers are as follows:

- AdventHealth Translational Research Institute (TRI) in Orlando, Florida
- ProSciento, Chula Vista, California

Estimated number of subjects at both sites combined: 20 T1DM and 9 Healthy

Estimated number of subjects at AdventHealth TRI site: 15 T1DM and 4 Healthy

Estimated number of subjects at ProSciento site: 5 T1DM and 5 Healthy

4.6 MULTI-SITE RESEARCH LOGISTICS/COMMUNICATION PLAN

AdventHealth Orlando Translational Research Institute will be the coordinating center and [name] will be the lead investigator for this study. As this is a multi-site study, the following processes will be put in place with all the participating centers:

- All sites will have the most current version of the protocol and consent document
- All required approvals will be obtained at each site (including approval by the site's IRB of record).
- All modifications will be communicated to sites and approved (including approval by the site's IRB of record) before the modification is implemented.
- All engaged participating sites will safeguard data as required by local information security policies.
- All local site investigators conduct the study appropriately.
- All non-compliance with the study protocol or applicable requirements will be reported in accordance with local policy.

Emails, Teams Meetings, and telephone calls will be used to communicate with all participating sites to address any study-related issues and to inform the sites on closure of the study. Interim analysis will not be performed.

5 STUDY POPULATION

5.1 INCLUSION CRITERIA

Type 1 diabetes cohort

1. Age 20-60 years
2. Diagnosis of T1DM according to American Diabetes Association (ADA) criteria continuously requiring insulin for survival
3. Diabetes diagnosis performed more than 5 years before enrollment
4. Fasting C-peptide levels < 0.7 ng/mL with a concurrent plasma glucose concentration > 90 mg/dL (Labs may need to be repeated if the Plasma glucose is \leq 90 mg/dL)
5. For female participants: must be > 6 months post-partum and not lactating and agrees not to become pregnant during the study and for at least 2 weeks after the last dose of the study medication. For male participants: agrees not to donate sperm or not to get a woman pregnant during the study and for at least 2 weeks after the last dose of the study medication.

Healthy subject cohort

1. Age 20-60 years
2. General good health
3. Creatinine clearance >80 mL/min based on CKD-EPI equation
4. Fasting blood glucose (FBG) >70 mg/dL and <100 mg/dL
5. No history of diabetes
6. For female participants: must be > 6 months post-partum and not lactating and agrees not to become pregnant during the study

5.2 EXCLUSION CRITERIA

An individual who meets any of the following criteria will be excluded from participation in this study:

1. BMI >35 kg/m² and <18.5 kg/m² for females and BMI >35 kg/m² and <20 kg/m² for males.
2. Increase or decrease body weight greater than 3kg in the 3 months before enrollment.
3. Evidence by history, ECG or exams of clinically significant cardiovascular disease (unstable angina, myocardial infarction or coronary revascularization within 6 months, clinically significant abnormalities on ECG, presence of cardiac pacemaker, implanted cardiac defibrillator)
4. Evidence of autonomic neuropathy
5. Liver disease (AST or ALT >2.5 times the upper limit of normal)
6. Kidney disease (creatinine >1.6 mg/dL or estimated GFR <60 mL/min).
7. Dyslipidemia, including triglycerides >500 mg/dL, LDL >200 mg/dL or unstable hyperlipidemia. Treatment with a single lipid lowering agents is allowed if stable within the previous 3 months.
8. Anemia (hemoglobin <12 g/dL in men, <11 g/dL in women)

9. Thyroid dysfunction (suppressed TSH, elevated TSH $<10 \mu\text{U}/\text{ml}$ if symptomatic or elevated TSH $>10 \mu\text{U}/\text{ml}$ if asymptomatic)
10. Uncontrolled hypertension (BP $>160 \text{ mmHg}$ systolic or $>100 \text{ mmHg}$ diastolic) or treatment with more than 2 antihypertensive medications.
11. Current use of beta-adrenergic blocking agents or their use was stopped less than one month before recruitment
12. History of cancer within the last 5 years (skin cancers, with the exception of melanoma, may be acceptable)
13. History of organ transplant
14. History of HIV, active Hepatitis B or C, or Tuberculosis
15. Pregnancy, lactation or 6 months postpartum from the scheduled date of screening lab collection
16. Females of childbearing potential (any female except those with tubal ligation, hysterectomy, or absence of menses >2 years) unwilling to use an approved method of contraception (one medically accepted method of contraception with $\ge 99\%$ effectiveness when used consistently and correctly). Male participants: he or he and his partner unwilling to use an approved method of contraception with $\ge 99\%$ effectiveness when used consistently and correctly
17. History of Major Depression in the last 5 years
18. History of an eating disorder
19. History of bariatric surgery
20. History of drug or alcohol abuse (≥ 3 drinks per day) within the last 5 years
21. Self-report of marijuana use ≥ 3 days/week in any form
22. Psychiatric disease prohibiting adherence to study protocol
23. Current use of oral or injectable anti-hyperglycemic agents: metformin, sulfonylureas, DPP IV inhibitors, SGLT-2 inhibitors, thiazolidinediones, acarbose, GLP-1 analogs
24. Initiation or change in hormone replacement therapy within the past 3 months (including, but not limited to thyroid hormone or estrogen replacement therapy). Hormone based contraception is acceptable.
25. Use of any medications known to influence glucose, fat and/or energy metabolism (e.g., growth hormone therapy, glucocorticoids [steroids], prescribed medications for weight loss, etc.). Patients on medications with acute effects on glucose metabolism used for other indications (certain antidepressants, ADHD and antiepileptic medications) may be enrolled if they have been on chronic, stable doses (≥ 6 months)
26. Uncontrolled seizure disorder
27. Current night shift worker
28. Presence of any condition that, in the opinion of the Investigator, compromises participant safety or data integrity or the participant's ability to complete study visits
29. Unwilling and/or unable to follow and comply with scheduled visits and protocol requirements

Additional exclusion Criteria for the type 1 diabetes cohort

1. HbA1c $>9\%$
2. Insulin dose less than 0.3 U/kg or low carbohydrate diet
3. History of T2DM or any form of diabetes other than T1DM
4. Hypoglycemia unawareness as assessed using the GOLD score
5. Using a predictive low blood glucose suspend mode on an insulin pump or a hybrid closed loop algorithm for insulin delivery. For those applying these strategies for everyday

management of blood glucose and willing to participate, the algorithm will be stopped at enrollment.

6. Two or more episodes of severe hypoglycemia (Hypoglycemia requiring help from a third party) per month in the past six months
7. One or more DKA episodes in the past 3 months
8. QTcF >450 msec for males and >470 msec for females
9. Using non-insulin agents to control blood glucose levels
10. History or evidence of moderate or severe end-organ diabetic complications of retinopathy, nephropathy or neuropathy. Proliferative diabetic retinopathy. Non-proliferative retinopathy and microalbuminuria will be allowed.

Additional exclusion Criteria for the healthy cohort

1. Insulin treatment

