- Creatinine clearance >80 mL/min based on CKD-EPI equation
- Fasting blood glucose (FBG) >70 mg/dL and <100 mg/dL
- No history of diabetes
- For female participants: agrees not to become pregnant during the study

T1DM subjects must be generally healthy, without clinical evidence of impaired adrenal, pituitary, or thyroid function, and without evidence of symptomatic autonomic neuropathy. The subjects should not have:

1. Evidence of moderate or severe end-organ diabetic complications of retinopathy, nephropathy or neuropathy; proliferative retinopathy. Non-proliferative retinopathy will be allowed as is microalbuminuria but subjects must have a GFR > 60 mL/min/m² by CKD-EPI.
2. Evidence by history, ECG or exam of clinically significant cardiovascular disease. Subjects must have a QTcF <450 ms for males and < 470 ms for females.
3. Body mass index outside the range of 18.5 – 30 kg/m² for females and 20-30 kg/m² for males. Weight must have been stable (± 3 kg) for at least the preceding 3 months.
4. Subjects can have stable hyperlipidemia and hypertension treated with no more than one lipid lowering medication or two antihypertensive medications. For each medication the dose should be stable for the past 3 months. Beta-adrenergic blocking agents will not be allowed during the study.
5. Hypoglycemia unawareness, as assessed by GOLD score at screening (1, 2). For this study, subjects with severe hypoglycemic episodes associated with seizure or coma within three months of screening or diabetic ketoacidosis within six months of screening will be excluded.
6. Predictive low blood glucose suspend mode on an insulin pump, or a hybrid closed loop algorithm for insulin delivery
7. Hba1c >9%
8. One or more DKA episodes in the past 3 months
9. Insulin dose less than 0.3 U/kg or on a low carbohydrate diet

Phase:	2a
Description of Sites/Facilities Enrolling Participants:	The study will be conducted at the AdventHealth Translational Research Institute (TRI) in Orlando, Florida, USA and ProSciento, Chula Vista, California, USA. Assays will be performed at the TRI, ProSciento laboratories, Scripps Mercy Hospital Laboratory, LabCorp and at Covance Laboratory Inc. (pharmacokinetic measures).

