MBX-2982 could potentially affect plasma glucose levels, causing either a reduction via incretin stimulation or an increase via glucagon stimulation. The participants will be instructed to check their blood glucose with a glucometer before meals and at bedtime. The participants will be instructed on signs and symptoms of hyper- or hypo-glycemia, and on appropriate treatment. To prevent the risk of DKA caused by a decrease of insulin due to incretin reduction of blood glucose and glucagon potentiation, subjects requiring less than 0.3 U/Kg/day of insulin, on a low carb diet or with an episode of DKA in the past three months will not be enrolled. Written instruction on sick day management and on management of unusual symptoms associated with alcohol intake, strenuous or prolonged activity will be provided. Urine ketone checks will be recommended when blood glucose is >250 mg/dl and whenever the participant is not feeling well. If small to moderate amounts of ketones are measured (small to moderate in the urine or blood β -hydroxybutyrate 0.6-1.5 mmol/L) the participants will be instructed to contact the research team, administer rapid-acting insulin, consume 15-30g of carbohydrate, hydrate with 300-500 ml of fluid hourly, check self-monitored blood glucose frequently and ketones every 3-4 hours. If trace ketones are present on more than 3 separate days in a 7-day period, the participant will be instructed to contact the study team, measure fasting ketone daily and hold the study medication.

Further mitigation of glucose excursions will be facilitated through the weekly review of the CGM patterns and adjustment of insulin doses. As much as possible, the basal insulin dose will be maintained at baseline levels to prevent DKA

Due to the unknown profile in elderly and children, these categories of participants will not be enrolled. Since no specific studies have been performed in patients with renal dysfunction or renal failure, only subjects with a glomerular filtration rate >60 ml/min will be enrolled.

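### Section 5.2 has no explicit exclusion for a recent hypoglycemic seizure or coma, although the synopsis excludes it; the synopsis's six-month DKA look-back is also out of line with the rest of the protocol

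*Combined protocol and SAP*

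**What the plan says.** The exclusions for the type 1 diabetes (T1DM) cohort appear twice.

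**Synopsis (Section 1.1).** Item 5 starts with hypoglycemia unawareness by GOLD score. A second sentence then adds a rule on history: "severe hypoglycemic episodes associated with seizure or coma within three months of screening or diabetic ketoacidosis within six months of screening will be excluded". Item 8 of the same list is a separate DKA rule with a three-month look-back.

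**Section 5.2.** The list opens with "An individual who meets any of the following criteria will be excluded from participation in this study", so each criterion is sufficient alone. The relevant entries are:

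- T1DM item 4: "Hypoglycemia unawareness as assessed using the GOLD score". The second sentence of synopsis item 5 is not carried over.
- T1DM item 6: "Two or more episodes of severe hypoglycemia (Hypoglycemia requiring help from a third party) per month in the past six months".
- T1DM item 7: "One or more DKA episodes in the past 3 months".
- General item 26: "Uncontrolled seizure disorder".
- General item 28, discretionary: "Presence of any condition that, in the opinion of the Investigator, compromises participant safety or data integrity".

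**Section 2.3.3.2** explains the DKA rule as protection against ketoacidosis if insulin doses fall on treatment. It says that subjects "on a low carb diet or with an episode of DKA in the past three months will not be enrolled".

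**The concern.** The two lists give different answers for a person with a recent hypoglycemic seizure or coma, and the list that omits this history is the detailed one in the body of the protocol. Staff who screen from Section 5.2 alone could pass someone whom the synopsis bars.

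That history bears directly on the study procedure. Under Section 8.2 each clamp brings glucose down to 50 to 55 mg/dL and holds it there for about 30 minutes, and each T1DM participant has two clamps. Section 2.3.1.1 lists seizure among the rare consequences of hypoglycemia during the clamp. Section 7.2.1 withdraws a participant after any Level 3 episode during treatment, so the protocol already treats a single severe event as decisive once treatment has begun.

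Two sites enroll under separate IRB oversight (Sections 4.5 and 10.4.1), so each could resolve the difference in its own way. The DKA look-back raises a smaller question of the same kind.

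**Working it through.** The plan states no figure on this point, so the check is a comparison of texts, run on four test candidates. Inputs are synopsis items 5 and 8, the Section 5.2 items listed above, and Section 2.3.3.2.

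| Candidate | Synopsis | Section 5.2, explicit criteria |
|---|---|---|
| A. One hypoglycemic coma two months before screening | Excluded (item 5) | Not excluded |
| B. Two assisted episodes in every one of the past six months, none with seizure or coma | No history rule applies | Excluded (T1DM item 6) |
| C. DKA four months before screening | Excluded by item 5, not by item 8 | Not excluded (T1DM item 7) |
| D. DKA two months before screening | Excluded (items 5 and 8) | Excluded (T1DM item 7) |

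**Candidate A against each Section 5.2 entry.**

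- Item 6 can be read in two ways. If any single month with two episodes excludes, the threshold is 2 in a month, and 1 < 2. If it means an average of two a month over six months, the threshold is 2 × 6 = 12, and 1 < 12. One episode passes under both readings.
- General item 26 concerns a seizure disorder, not a seizure or coma caused by low glucose.
- T1DM item 4 measures awareness by GOLD score. It may or may not pick up this person. Synopsis item 5 names GOLD and then adds the seizure-or-coma rule, so the synopsis did not rely on GOLD alone.
- General item 28 allows exclusion at the investigator's discretion but does not require it.

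No explicit criterion is met. Candidate A alone establishes the gap.

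**Candidate B.** The mismatch also runs the other way: the synopsis has no counterpart to item 6.

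**DKA.** Four places give a look-back. Synopsis item 8, Section 5.2 item 7 and Section 2.3.3.2 say three months; synopsis item 5 says six. The disagreement covers 6 − 3 = 3 months, into which candidate C falls. Section 5.2 agrees with the majority, and the six-month figure stands alone.

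**Amendment history (Section 11).** The printed entries are V3.0, V4.0, V5.0, V7.0, V8.0 and V9.0. None of the six removes the seizure-or-coma rule or changes a DKA window. None records item 6 being added either.

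**Who can still be affected.** The V8.0 entry speaks of 10 T1DM participants completed, of 20 planned. That left at most 20 − 10 = 10 planned participants at that time, and V9.0 came later.

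**The case against.** The strongest reply is that the lists can be read together. Synopsis item 5 says outright that these people are excluded, and Section 8.1.2 schedules only candidates who meet all enrollment criteria. On that reading candidate A never enters. This is fair as far as it goes: the gap opens only if a site works from Section 5.2 alone. But that is the section with the full criteria, and a safety exclusion should not depend on staff also consulting the summary.

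Second, item 6 may have been meant to replace the seizure-or-coma wording. This cannot be ruled out. Synopsis eligibility text can be out of date: its BMI ceiling is 30 kg/m², while Section 5.2 has 35. A reader might infer from the silent amendment log that the criterion was dropped by accident. The log does not support that. V2.0 and V6.0 are not listed, the current summary of changes is not among the pages available, and the log is equally silent on the origin of item 6.

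Third, clamp safeguards are substantial. A clinician is at the bedside and severe effects are corrected with intravenous glucose (Section 2.3.3.1). Glucose is measured every 5 minutes, dextrose can be started early to prevent overshoot, and safety glucose is available in recovery (Section 8.2). A clamp may be rescheduled to give at least 5 days free of glucose below 55 mg/dL (Sections 8.1.6 and 8.1.10). These measures lower the risk for those enrolled, but they do not decide who enrolls.

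Two further readings go too far. Item 6 arithmetically lets through 3 episodes in three months at one a month, or 11 on the averaging reading if all cluster late. Those are extremes that GOLD and investigator judgement would also have to miss, and they do not measure the problem. Nor does Section 5.2 depart from the synopsis as a whole on DKA, because it matches synopsis item 8.

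**Conclusion.** The seizure-or-coma conflict is real and should be corrected. A person with one recent hypoglycemic seizure or coma is barred by the synopsis and by no explicit criterion in Section 5.2, with only partial backstops before two clamps at 50 to 55 mg/dL. The conclusion rests on the current wording of the two lists and does not depend on how item 6 is read.

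The DKA difference is a secondary matter of harmonisation, with one outlying figure in synopsis item 5.

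The documents do not establish which text was intended, and they do not show that any such person was or will be enrolled. They give no count of affected candidates, and none is assumed. Adding the criterion is recommended because it is the protective choice and already the sponsor's own wording, not because the omission is proven to be an error. Sample size, power and the primary analysis are not affected.

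**What to change.** 1. Add to the T1DM exclusions in Section 5.2: any severe hypoglycemic episode with seizure or coma during the three months before screening. Keep item 6.
2. Repeat item 6 in the synopsis, so that both lists carry the same two rules on severe hypoglycemia.
3. Change the DKA look-back in synopsis item 5 to three months, matching the other three places. If the sponsor deliberately wants six, use six in all four.

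No withdrawal or stopping threshold needs to change.

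**Cost.** One amendment of wording, with IRB approval under Section 10.4.1. The first edit adds at most a few screen failures among people not yet enrolled, all of whom the synopsis already excludes. The second restates an existing Section 5.2 rule. Setting three months for DKA gives up the longer look-back in synopsis item 5; setting six would turn candidates with DKA three to six months before screening into screen failures under Section 5.2. The practical benefit shrinks as enrollment nears completion, but both sites and the final report still need one rule.
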